**Aim 2: Pilot CETA delivery at two Zambian HIV clinics (Stage 1B).** Hypothesis 1: *BI+CETA will be clinically ( $d>0.5$ ) and statistically ( $p<.05$ ) more effective in reducing alcohol use and comorbidities than BI alone.* Hypothesis 2: *ART retention and HIV viral load (VL) will improve among recipients of BI+CETA compared to BI alone ( $p<.05$ ).* To test these hypotheses, PLWH who screen positive for hazardous alcohol use will be enrolled. Those with comorbidities and/or who meet criteria for moderate-to-severe alcohol use disorder (AUD) ( $n=160$ ) will be randomized 1:1 to receive BI+CETA or BI alone. Participants who have hazardous alcohol use but do not have a moderate-to-severe AUD and do not have mental health comorbidities will receive a BI and be assessed but not included in the pilot RCT (they will be included in the 'cohort' study). We will measure the difference in change in alcohol use and comorbidities from enrollment to 6-months follow-up and use an Ethyl glucuronide test to confirm self-reported alcohol abstinence. ART retention and VL will also be measured at enrollment and 6 months.

**Aim 3: Investigate feasibility, acceptability, and other implementation factors related to delivery of BI and CETA.** We will describe the care cascade of this approach and identify demographic, clinical, and structural correlates of uptake, engagement, and completion of the BI and CETA. We will investigate implementation factors through mixed methods interviews with study participants and health workers.

**II. Background and Rationale:** Explain why this study is being done. Summarize briefly what is already known about the issue and reference previously published research, if relevant.

- Hazardous alcohol use is common and increasing among persons living with HIV (PLWH) in sub-Saharan Africa (SSA). Alcohol is the most commonly consumed and distributed substance in SSA and prevalence of alcohol consumption is increasing rapidly. PLWH face many adversities, including low social support, trauma exposure, and stigma that increase their risk for hazardous alcohol use and they are between two and four times more likely than the general population to have an alcohol use disorder (AUD).

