number of PLWH participants in Stage 1A will be n=32. Additionally, we will conduct 4 FGDs with health workers at our study clinics. These FGDs will also have a maximum number of 8 participants per group, thus the maximum number of healthcare worker participants will be n=32. Finally, we will conduct up to 16 key informant interviews with policy officials and relevant program leaders.

Stage 1B: This stage will enroll n=320 participant who have hazardous alcohol use: n=160 will formally be enrolled in the RCT (participants who meet criteria for a moderate-to-severe AUD or have hazardous alcohol use plus comorbidities) and n=160 who will not be enrolled in the RCT but will receive the BI and will be tracked for follow-up in a cohort study (participants with hazardous use but do not have a moderate-to-severe AUD and have no comorbidities).

The primary endpoint of the pilot RCT is the difference in change in AUDIT score from baseline to 6-month follow-up between BI+CETA and BI alone (see assessments section below). We believe that an effect size of CETA  $\geq 0.5$  would be clinically significant and justify further investigation in a subsequent latter Stage trial. Further assuming  $\alpha=0.05$  and  $\beta=80\%$ , we will require a total sample size of 128 (n=64 per arm). To account for possible loss-to-follow-up/drop-out of 20% based on our previous studies with HIV-affected populations in Zambia, we will inflate the sample size to 160 (n=80 per arm). Based on Preliminary Studies, we anticipate that 20% of female and 40% of male patients at the study sites will report hazardous drinking and that 50% of hazardous drinkers will qualify for the RCT. Therefore, we expect to enroll n=320 hazardous drinkers to reach the RCT target sample size. There is no sample size calculation for cohort study participant; however, the anticipated sample of n=160 should be sufficient to detect even a small within-group change in outcomes after receipt of BI.

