### Interventions

- World Health Organization mhGAP BI. All participants (regardless of whether RCT criteria are met) will receive a BI. We will provide training to lay counselors (e.g., counselors/nurses already working in the HIV clinics) based on World Health Organization (WHO) mhGAP-Intervention Guide (mhGAP-IG). The mhGAP-IG was developed to provide non-specialists in LMIC with knowledge and skills to deliver low-intensity interventions with fidelity in primary care to treat mental, neurological, and substance use problems. WHO has developed modules to train health care workers. The JHU clinical team in Zambia will adapt these modules to provide a 2-day workshop for counselors at our two clinics. Training will cover components such as: (1) psychoeducation (e.g., examples of ways that hazardous use can be reduced); (2) engagement (e.g., discussing motivations for drinking); (3) personalized feedback and advice (e.g., helping the participant reflect on how use is impacting their life); and (4) encouragement for the participant to change their pattern of use.

Following the baseline assessment, the assessor will notify the on-duty counselor who has been trained in the BI. The BI, which is expected to take 10-15 minutes, will be offered to participants the same day and provided in a private room.

- [Common Elements Treatment Approach \(CETA\)](#). Lay counselors (e.g., HIV peer educators, counselors in the HIV clinics) will be trained to deliver CETA to participants randomized to BI+CETA (i.e., n=80). After enrollment, participants receiving CETA will flexibly meet with their counselor weekly for approximately one-hour sessions, for 6-12 weeks depending on presentation and symptom level. Core elements of CETA sessions are described in Table 2 and will be adapted as needed in Stage 1A.

**Table 2.** Common Elements Treatment Approach

Component	Content	Target
Engagement	Discuss how program helps Identify obstacles to engagement	Promote client buy-in
Safety	Assess client risk for harm to self/others Domestic violence/abuse assessment Initiate safety plan as needed	Assess and address client safety
Empirically-supported cognitive-behavioral elements		
Psychoeducation/Introduction	Program information, normalize symptoms, goal setting	Psychoeducation Reduce stigma

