Study Phase	Activity	Year 1				Year 2				Year 3			
		Q 1	Q 2	Q 3	Q 4	Q 1	Q 2	Q 3	Q 4	Q 1	Q 2	Q 3	Q 4
Planning	Study protocol finalization and ethical approval												
	Staff hiring and site preparation												
	Training of qualitative data staff												
Stage 1A	Focus groups and key informant interviews												
	Adaptation of CETA for PLWH												
	Development of CETA protocol in HIV care based on Stage 1A												
	CETA/mhGAP-IG trainings, assessor trainings, M&E trainings												
Stage 1B	CETA pilot cases												
	Recruitment, consent, screening and baseline assessments (ACASI, HIV)												
	Interventions active												
	Post-treatment assessments (ACASI, UEtG)												
	6-month outcomes assessment (ACASI, UEtG, HIV outcomes via chart review)												
Analysis, dissemination, and next steps	Implementation data collection (PLWH, clinic staff, policy officials)												
	Data analysis												
	Report/manuscript writing and dissemination at conferences												
	Preparation and submission of follow-up R01												

- Provide a brief data analysis plan and a description of variables to be derived.

*Analysis of treatment uptake and completion.* We will estimate a logit model with a binary outcome (1=completer; 0=non-completer) to assess predictors of treatment completion. Predictors will be demographic (e.g., sex, age), clinical (e.g., symptom severity), and structural (e.g., distance from clinic) level factors.

*Analysis of ACASI outcome data.* Analyses will be intent-to-treat. AUDIT score, along with other continuous secondary outcomes (Past 30-Day TLFB [% days drinking and mean drinks per day], CES-D, HTQ, ASSIST scores) will be modelled with linear mixed models. Fixed effects will include treatment arm (0=BI; 1=BI+CETA), time (0=Baseline; 1=6-months post-baseline), and interaction terms between treatment arm

and time. This will allow estimation of the mean difference in change in score between arms and 95% confidence intervals. Cohen's D will be calculated to estimate effect size. Covariates will be included if they differ meaningfully at baseline or predict significant change in the outcome. For dichotomous outcomes or non-normally distributed continuous outcomes, generalized linear mixed effects models will be estimated. Paired t-tests will be used to assess within group change among the non-Pilot RCT hazardous drinkers.

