*Analysis of implementation data.* Mixed methods analysis based on NIH best practice guidelines will be used to integrate findings from the quantitative and qualitative data. Descriptive analyses will be used to investigate the quantitative data on constructs of acceptability, appropriateness, reach, feasibility, and cost. The qualitative data will provide in depth understanding of factors related to (1) mechanisms of change; and (2) barriers and facilitators to program implementation in the Zambian context. Findings will be shared with local (HIV clinics, Lusaka district, and Zambia MoH) and international stakeholders (PEPFAR/CDC, UNAIDS, etc.) to inform future programming efforts.

5. **Answer the following if they are relevant to your study design:**

1. If the study has different arms, explain the process for assigning participants (intervention/control, case/control), including the sequence and timing of the assignment.

The assessor will have two locked cabinets at the clinic with sealed envelopes. One cabinet will contain randomization assignments for female participants, the other for male participants. Printed on the outside of the sealed envelopes will be a Randomization ID. When a participant is eligible for the pilot RCT, the assessor will retrieve the next available envelope and record the Randomization ID and Screening ID on a Screening Information Sheet, thus linking the two IDs to the participant. Randomization IDs will be assigned to BI+CETA or BI alone using *randomize* in Stata *a priori* by a U.S.-based statistician not affiliated with the study. Randomization IDs will be randomized 1:1 in blocks of 20 stratified by sex. The assessor will inform the participant of their assignment by opening the envelope

immediately after the baseline assessment. This ensures that the assessor is blinded to the participant's randomization status during the assessment itself. Follow-up assessments will be conducted by a different assessor.

2. If human biospecimens (blood, urine, saliva, etc.) will be collected, provide details about who will collect the specimen, the volume (ml) and frequency of collection, how the specimen will be used, stored, identified, and disposed of when the study is over. If specimens will be collected for use in future research (beyond this study), complete the "Biospecimen Repository" section below.

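### The primary AUDIT analysis and the 80% power leave out CETA counsellor clustering, so for any positive counsellor ICC the interval is too narrow, by an amount the documents cannot fix

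*Combined protocol and SAP*

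**What the plan says.** The primary endpoint (section III.B) is the "difference in change in AUDIT score from baseline to 6-month follow-up between BI+CETA and BI alone". Hypothesis 1 under Aim 2 expects BI+CETA to be "clinically ( $d>0.5$ ) and statistically ( $p<.05$ ) more effective" than BI alone, so this is a formal test although the study is a pilot.

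Section III.B takes an effect size of 0.5, alpha 0.05 and 80% power (printed as beta) and concludes "we will require a total sample size of 128 (n=64 per arm". It allows for 20% loss to follow-up: "we will inflate the sample size to 160 (n=80 per arm". It mentions no ICC, design effect or number of counsellors.

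The data analysis plan in section V (Analysis of ACASI outcome data) uses linear mixed models: "Fixed effects will include treatment arm (0=BI; 1=BI+CETA), time (0=Baseline; 1=6-months post-baseline), and interaction terms between treatment arm" and time. Random effects are not stated. No counsellor term, clinic term, cluster-robust variance or clustering sensitivity analysis appears anywhere.

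On delivery, section V (Interventions) has lay counsellors treating the 80 BI+CETA participants, and "participants receiving CETA will flexibly meet with their counselor weekly" for about an hour over 6-12 weeks. Both arms get one 10-15 minute BI from the on-duty counsellor. Assignment is of individuals: "Randomization IDs will be randomized 1:1 in blocks of 20 stratified by sex".

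**The concern.** Eighty participants at two clinics, treated by a pool of lay counsellors, will share counsellors. If counsellors differ in how well they deliver CETA, outcomes of people with the same counsellor are correlated, and the CETA arm carries less information than its head count suggests. A standard error that ignores this is too small. The 95% interval then covers less than 95%, and the p<.05 test can reject too often. The result is meant to decide whether a later trial is justified. If counsellor identity is not recorded, the ICC that such a trial would need for its design cannot be estimated.

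**Working it through.** **Inputs from the documents.** d = 0.5 (so SD = 1), alpha 0.05, 80% power, 64 evaluable and 80 randomised per arm, 1:1 allocation. Sidedness is not stated. Two-sided is assumed because one-sided would need only 50 per arm.

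**Assumed inputs.** k = 4, 8 or 16 counsellors with equal caseloads; ICC 0.01-0.10 on the scale on which d is standardised; full CETA uptake unless stated; no extra clustering in the BI arm.

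**1. The plan's own figure.** A two-sided two-sample t-test with 64 per arm has noncentrality 0.5 × √(64/2) = 2.83 on 126 df and power 80.1%. With 63 per arm it is 79.5%. Dropout: 128/0.8 = 160. Both figures reproduce under independence, with nothing to spare.

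**2. Standard error with counsellors in the CETA arm.** Caseload m = 64/k; design effect DE = 1 + (m − 1) × ICC; variance of the difference = (DE + 1)/64, against 2/64 under independence. The ratio of standard errors is √((DE + 1)/2).

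Example, k = 8 and ICC 0.05: m = 8, DE = 1 + 7 × 0.05 = 1.35, ratio √(2.35/2) = 1.084.

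**3. Size of the unadjusted test.** Type I error ≈ 2 × (1 − Φ(1.96/ratio)). For the example, 1.96/1.084 = 1.81, giving 7.1%.

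**4. Power of a test that allows for counsellors.** Noncentral t with noncentrality 0.5/SE and Satterthwaite df = (DE + 1)² / (DE²/(k − 1) + 1/63). For the example, SE = √(2.35/64) = 0.192, noncentrality 2.61, df 20.0, power 69.9%.

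| Counsellors | ICC | SE ratio | Type I error, unadjusted | Power, adjusted |
|---|---|---|---|---|
| 8 | 0 | 1.000 | 5.0% | 77.6% |
| 8 | 0.01 | 1.017 | 5.4% | 76.0% |
| 8 | 0.05 | 1.084 | 7.1% | 69.9% |
| 8 | 0.10 | 1.162 | 9.2% | 63.1% |
| 4 | 0.01 | 1.037 | 5.9% | 69.3% |
| 4 | 0.05 | 1.173 | 9.5% | 55.2% |
| 4 | 0.10 | 1.323 | 13.8% | 43.2% |
| 16 | 0.01 | 1.007 | 5.2% | 78.5% |
| 16 | 0.05 | 1.037 | 5.9% | 76.1% |
| 16 | 0.10 | 1.072 | 6.8% | 73.1% |

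Simulation of the unadjusted t-test with 8 counsellors agrees (5.3%, 6.9% and 9.3% at ICC 0.01, 0.05 and 0.10). Coverage of the nominal 95% interval is 100% minus the type I column.

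**5. Splitting the power loss.** At 8 counsellors, 80.1% − 77.6% = 2.5 points come from having few clusters, even at ICC 0. The unadjusted test still rejects about 78% of the time at d = 0.5 and ICC 0.05. Its fault is therefore in coverage and type I error far more than in rejection rate.

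**6. Incomplete uptake.** If a fraction p start CETA and non-starters are unclustered, DE = 1 + p × (64p/k − 1) × ICC. With k = 8 and ICC 0.05, p = 0.8 gives DE = 1.216 and type I error 6.3%; p = 0.6 gives DE = 1.114 and 5.7%.

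**7. No dropout.** With 80 per arm, 8 counsellors and ICC 0.03, DE = 1 + 9 × 0.03 = 1.27, SE = √(2.27/80) = 0.168 and power is 80.8%.

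**The case against.** Several points on the other side stand.

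- **The model is underspecified; it does not declare independence.** It is a mixed model whose random part is unstated. A reader might infer that the plan asserts independence between all participants. It does not; what can be said is that no counsellor term is planned. With two time points the obvious random effect is the participant, which would not capture counsellors.
- **Power.** A reader might infer that 80% is missed unless the counsellor effect is exactly zero. The figures do not support that. Part of the shortfall is the degrees-of-freedom penalty, which is there at zero ICC. By normal approximation an ICC up to about 0.005 with 8 counsellors keeps 80% at 64 per arm, and with no dropout 80% survives to an ICC of about 0.03.
- **The BI arm.** It is not free of counsellor contact. On-duty counsellors deliver the BI to everyone, and section VII (Emotional distress) adds weekly safety calls, with counsellor home visits for non-response. The imbalance between arms is in intensity.
- **Uptake.** Analysis is intent-to-treat, and counsellors stop trying to engage participants who have not started within a month. Non-starters dilute the clustering.
- **The null.** Randomisation is individual. If CETA did nothing for anyone, the unadjusted test would keep its size. Inflation needs counsellor effects that vary around zero. Loss of coverage is not confined to that null: it follows whenever counsellors vary and the inference is meant to reach beyond those in the study.

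None of this reverses the direction, and nothing elsewhere in the plan supplies the missing term. The covariate rule cannot, because BI-alone participants have no CETA counsellor.

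**Conclusion.** The concern holds as an omission in the primary model and an unstated assumption behind the 80%. For any positive counsellor ICC, an interval computed without a counsellor term is too narrow. At 64 evaluable per arm, full uptake and 8 counsellors, ICC 0.01-0.10 gives a standard error 2-16% too small relative to the independence value, type I error 5.4-9.2%, and adjusted power 76-63%. With 16 counsellors or incomplete uptake the effect is smaller, and at low ICC it is slight. With 4 counsellors it is larger. The number of counsellors, the ICC and uptake are all assumed here, so the direction is firm and the size is not. The high end (about 14% type I error) needs 4 counsellors, ICC 0.10 and full uptake together and should not be read as the expected case. The change is worth making because it is cheap and counsellor identity may not be recoverable afterwards.

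**What to change.** 1. Record the counsellor ID for every CETA participant as treatment is delivered.
2. In the ACASI outcome analysis, specify a partially nested mixed model: random participant effect, random counsellor effect in the CETA arm only, Satterthwaite or Kenward-Roger degrees of freedom, clinic as a fixed effect, and CETA non-starters treated as unclustered.
3. State a fallback for a counsellor variance estimated at zero. This will be common: with 8 counsellors of 8 participants, the between-counsellor mean square is no larger than the within-counsellor one in about half of trials at ICC 0.01 and a third at ICC 0.05 (F on 7 and 56 df).
4. Report the estimated ICC with its interval for the later trial.
5. In section III.B, say that 80% power assumes no counsellor clustering, and give power for the planned number of counsellors over a range of ICCs.

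How cases are allocated to counsellors should stay as it is. Changing it to suit the analysis would alter delivery in a pilot meant to reflect real-world practice.

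**Cost.** One recorded variable and a few sentences. The interval is wider, and stated power falls from 80.1% by about 4-17 points with 8 counsellors over ICC 0.01-0.10 (about 2-7 with 16, about 11-37 with 4). No participants are added, but 80% is then not restored: with 8 counsellors and ICC 0.05 that would need 88 evaluable per arm, or 2 × 88/0.8 = 220 randomised. For a pilot, stating the lower power plainly is enough.

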1. Will the study staff be blind to participant intervention status?

Assessors will be blind to participant intervention status. Due to the nature of the interventions, counselors will not be blinded. Data Analysts will also be blinded.

2. Will participants receive standard care or have current therapy stopped?

Participants are already receiving standard of HIV care in Zambia and this will be continued during and after the study. Participants will not be asked to stop any current therapy.

3. Will you use a placebo or non-treatment group, and is that justifiable?

We will not have a non-treatment group. The control group will receive the BI, which is the current standard of care at HIV clinics in Zambia.

4. Explain when you may remove a participant from the study.

Participants will be temporarily removed from the study if they demonstrate actively suicidal or homicidal thoughts. Anyone who develops psychosis in need of hospitalization will also be removed. In any of these events, research assistants, counselors, and supervisors will work together to get appropriate psychiatric assistance for the individual. The study PI and our clinical supervisory team will consult with psychiatric providers in Zambia to determine whether the participants may return to the study following appropriate treatment.

Participants will be removed from the study at their request if they express to us that they do not feel safe.

5. What happens to participants on study intervention when the study ends?

Study interventions will be completed before the end of the study. Following the end of the study, participants who request additional services will be referred to appropriate care.

6. Describe the process for referring participants to care outside the study, if needed.

Some participants may experience emotional distress as a result of participation. Many therapeutic interventions deal with small degrees of stress within a session as part of the treatment. Based on research and experience, the expected degree of distress will be minimal and expected as part of the therapeutic process. In cases where distress does occur during treatment, the participant would be with a trained counselor who will be trained at handling such situations. In addition, these

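### The primary AUDIT model is an unadjusted difference in change, with baseline AUDIT and sex not pre-specified and an open covariate rule: valid, but it gives up precision

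*Combined protocol and SAP*

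**What the plan says.** Section III.B (sample size) defines the outcome: "The primary endpoint of the pilot RCT is the difference in change in AUDIT score from baseline to 6-month follow-up", comparing BI+CETA with BI alone. It takes a standardised effect of 0.5 and 80% power at alpha 0.05, and arrives at 64 per arm, raised to 80 per arm for 20% dropout.

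The data analysis plan in Section V (Analysis of ACASI outcome data) specifies an intent-to-treat linear mixed model: "Fixed effects will include treatment arm (0=BI; 1=BI+CETA), time (0=Baseline; 1=6-months post-baseline), and interaction terms between treatment arm" and time. It adds: "This will allow estimation of the mean difference in change in score between arms and 95% confidence intervals". Then: "Cohen's D will be calculated to estimate effect size". The SD used to standardise is not stated. Further terms are covered only by: "Covariates will be included if they differ meaningfully at baseline or predict significant change in the outcome".

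On allocation, Section V says: "Randomization IDs will be randomized 1:1 in blocks of 20 stratified by sex". Sex is not a named term in the outcome model; in the analysis plan it appears only as an example predictor of treatment completion. On blinding: "Data Analysts will also be blinded".

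**The concern.** Baseline AUDIT is in the model only as the time-0 response. Because arm has its own main effect, the baseline means of the two randomised arms are free to differ, and any chance difference is carried at full weight into the difference in change. Conditioning on baseline, or constraining the baseline means to be equal, avoids this and usually gives a narrower interval for the same treatment effect. The plan does neither, and it omits the factor on which randomisation is stratified.

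The covariate sentence does not close the gap. It gives no candidate list, no meaning for a meaningful baseline difference, and no form of entry. Form matters: a covariate added only as a time-invariant main effect leaves arm-by-time essentially unchanged, while a covariate-by-time term changes it. Two analysts following the text could report different primary results.

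At stake are the width of the primary confidence interval and the certainty that the primary model was fixed before the data were seen.

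**Working it through.** **Inputs from the documents.** d = 0.5, alpha 0.05, power 80%, 64 per arm evaluable, 80 per arm randomised, 20% dropout (Section III.B). Model terms as quoted above.

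**Assumptions.** The baseline to 6-month correlation (rho) and both SDs are not given. I use rho = 0.3, 0.5, 0.7 and r = baseline SD / 6-month SD = 1, 0.85, 0.7. Values of r below 1 are plausible because entry sets a minimum AUDIT score (Section IV).

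**Step 1: the plan's own figure.** A two-sided two-sample t-test with d = 0.5 needs 63.8 per arm for 80% power, so 64 reproduces. 128/(1 − 0.2) = 160 also reproduces. A one-sided test would need 50 per arm, so the plan's figure is two-sided.

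**Step 2: what the model estimates.** In one simulated complete data set (n = 128, rho 0.5), the mixed model's arm-by-time term was −2.183 (SE 1.033), the same as a comparison of change scores (−2.183, SE 1.033). Adjusting for baseline gave SE 0.839. Adding sex on top of baseline gave 0.840.

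**Step 3: variance.** In units of the 6-month variance:
- change: 1 + r² − 2·rho·r
- baseline-adjusted: 1 − rho²
- change minus adjusted: (r − rho)², which is never negative

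| r | rho | change | adjusted | variance saved | adjusted completers per arm matching 64 |
|---|---|---|---|---|---|
| 1 | 0.3 | 1.40 | 0.91 | 35% | 42 |
| 1 | 0.5 | 1.00 | 0.75 | 25% | 48 |
| 1 | 0.7 | 0.60 | 0.51 | 15% | 54 |
| 0.85 | 0.3 | 1.21 | 0.91 | 25% | 48 |
| 0.85 | 0.5 | 0.87 | 0.75 | 14% | 55 |
| 0.85 | 0.7 | 0.53 | 0.51 | 4% | 61 |
| 0.7 | 0.3 | 1.07 | 0.91 | 15% | 54 |
| 0.7 | 0.5 | 0.79 | 0.75 | 5% | 61 |
| 0.7 | 0.7 | 0.51 | 0.51 | 0% | 64 |

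The last column is 64 × adjusted/change, rounded. The interval narrows by 1 − √(adjusted/change): 19%, 13% and 8% for r = 1; 8%, 3% and 0% for r = 0.7.

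**Step 4: power at 64 per arm, d = 0.5** (rho 0.3 / 0.5 / 0.7).
- d scaled on the change-score SD: the written model has 80% throughout. Adjusted: 94 / 90 / 86% (r = 1); 86 / 82 / 80% (r = 0.7).
- d scaled on the 6-month SD, r = 1: written 66 / 80 / 95%, adjusted 84 / 90 / 98%.
- d scaled on the 6-month SD, r = 0.7: written 77 / 88 / 98%, adjusted 84 / 90 / 98%.

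On the 6-month scale the written model falls below 80% only where the change variance exceeds 1, that is rho < r/2: below 0.50 for r = 1 and below 0.35 for r = 0.7.

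**Step 5: form of entry, sex and dropout.** 1,000 simulated trials, all parameters assumed: 160 randomised within sex, 80 per sex; SD 6 at both visits; rho 0.5; sex difference 4 at both visits; arm effect −3; a covariate adding 2 points per SD to 6-month AUDIT.

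| Model | SD of estimate, complete data | SD of estimate, 20% of follow-up missing |
|---|---|---|
| Arm, time, arm-by-time | 1.006 | 1.110 |
| + covariate main effect | 1.006 | 1.107 |
| + covariate and covariate-by-time | 0.951 | 1.052 |
| Common baseline mean | 0.902 | 1.018 |
| Common baseline mean + sex, sex-by-time | 0.901 | 1.018 |

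All models were unbiased (means −3.01 to −3.03). Relative to the model with no covariates, the main effect shifted the estimate by an average of 0.000 points (0.03 with missing data). Covariate-by-time shifted it by 0.26 (0.29), and by at most 1.3 (1.4).

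**Step 6: error rate of the covariate rule.** Null simulation with n = 128, 5 or 10 assumed prognostic covariates and 4,000 runs per setting. Type I error was 4.4–5.1% unadjusted, 4.1–4.9% with the rule applied mechanically, and 6.3–8.3% if the analyst could take the best of four readings.

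**The case against.** The strongest reply is that the plan's second criterion, predicting change, would itself bring in baseline AUDIT when it matters. The proportional saving equals the squared correlation between baseline and change: 0.5² = 25% at r = 1, rho 0.5, and 0.225² = 5% at r = 0.7, rho 0.5. With 128 completers those correlations would give t of about 6.5 and 2.6, so a rule that tested baseline AUDIT would usually select it. That criterion also points naturally to a covariate-by-time term. This would hold if baseline AUDIT were a candidate. The plan does not say that it is, and it is already a response in the same model, where entering it again as a covariate is awkward. The baseline-difference criterion leaves the form open in any case.

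Other points stand and set the weight:
- Sex has no measurable effect on precision (0.902 to 0.901), and omitting it does not bias the estimate.
- Restricted entry may put the trial at the low-gain end, where the saving reaches 0%.
- With d on the change-score scale there is no power shortfall.
- The simulated saving at rho 0.5 is 1 − (0.902/1.006)² = 20% with complete data and 1 − (1.018/1.110)² = 16% with 20% missing, below the 25% in the equal-SD table. Part of the gap arises because the extra covariate adds variance at 6 months only.
- Applied mechanically, the rule controls type I error, and blinded analysts cannot easily pick the most favourable reading. Blinding does not decide which covariates enter.

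This is a pilot with a brief analysis plan, but Aim 2 states a hypothesis of d > 0.5 and p < .05 on alcohol use, and Section III.B powers for it.

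**Conclusion.** The concern holds. The primary analysis is unbiased, matches the stated endpoint, and its sample size reproduces. It is nevertheless an unadjusted difference in change, and its final covariate set is left open.

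Over the assumed range of rho and SD ratio, baseline adjustment saves between 0% and 35% of the variance. Apart from a negligible small-sample cost, it loses nothing in that range. A shortfall below 80% power arises only if d is scaled on the 6-month SD and rho is below half the SD ratio. The gain comes from baseline AUDIT; the reason to include sex is that it stratifies the randomisation. This should be changed, but the trial's validity does not depend on it.

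**What to change.** Pre-specify the primary model as a linear mixed model for AUDIT with a common baseline mean: time and arm-by-time without an arm main effect, plus sex and sex-by-time, with unstructured covariance. Its arm-by-time term estimates the same difference in change as the stated endpoint, and participants with missing follow-up stay in the analysis. ANCOVA of 6-month AUDIT on arm, baseline AUDIT and sex is the complete-data counterpart.

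Use the same form for CES-D, HTQ and ASSIST where linear models apply, and the analogous baseline- and sex-adjusted generalized model where the plan calls for one. State which SD standardises Cohen's d. Confine the covariate rule to a labelled sensitivity analysis with a named candidate list and covariate-by-time terms.

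The cost is a few sentences in the analysis plan. Baseline AUDIT and sex are already collected on everyone, and no visit, measure or sample-size change is needed.
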